8.2 Recording of Adverse Events

At each contact with the subject, the investigator must seek information on adverse events by specific questioning and, as appropriate, by examination. Information on all

CONFIDENTIAL

adverse events will be recorded immediately in the source document, and also in the appropriate adverse event module of the case report form (CRF). All clearly related signs, symptoms, and abnormal diagnostic procedures results will be recorded in the source document, though should be grouped under one diagnosis.

All adverse events occurring during the study period must be recorded. The clinical course of each event will be followed until resolution, stabilization, or until it has been determined that the study treatment or participation is not the cause. Any serious adverse event that occurs after the study period and is considered to be possibly related to the study treatment or study participation should be recorded and reported immediately.

8.3 Reporting of Serious Adverse Events

8.3.1 Study Sponsor Notification by Investigator

A serious adverse event must be reported by telephone within 24 hours of finding out of the event. A Serious Adverse Event (SAE) form must be completed by the investigator and faxed to the study sponsor within 24 hours. The investigator will keep a copy of this SAE form on file at the study site. Report serious adverse events by phone and facsimile to:

University of Minnesota, Office of the Vice President of Research
[contact]
[contact]

Minnesota Medical Foundation
[contact]
[contact]

At the time of the initial report, the following information should be provided:

- Study identifier
- Study Center
- Subject number
- Name of the drug/device
- A description of the event
- Date of onset
- Current status (on-going, resolved)
- Whether study treatment was discontinued
- The reason why the event is classified as serious
- Investigator assessment of the association between the event and study treatment

Within the following 48 hours, the investigator must provide further information on the serious adverse event in the form of a written narrative. This should include a copy of the completed Serious Adverse Event form, and any other diagnostic information that will assist the understanding of the event. Significant new information of ongoing serious adverse events should be provided promptly to the study sponsor.

CONFIDENTIAL

8.3.2 IRB Notification by Investigator

Reports of all serious adverse events (including follow-up information) must be submitted to the IRB within 10 working days if it falls under the UPIRTSO guidelines.

8.3.3 FDA Notification by Sponsor

The study sponsor shall notify the FDA by telephone or by facsimile transmission of any unexpected fatal or life-threatening experience associated with the use of the drug as soon as possible but no later than 7 calendar days from the sponsor's original receipt of the information.

If a previous adverse event that was not initially deemed reportable is later found to fit the criteria for reporting, the study sponsor will submit the adverse event in a written report to the FDA as soon as possible, but no later than 15 calendar days from the time the determination is made.

8.4 Stopping Rules

Adolescents will enter continuation treatment at week 16. Assessments will be conducted at week 24 and 32. The adolescent completes the BDI-II at each therapy session, and therapists assess suicidality and change in adolescents' clinical status using the CGI-I and CGI-S at each therapy session. The subject will be evaluated by *an independent safety monitor* if at any time any of the following occur: 1) a suicide attempt, 2) serious suicidal ideation (with a plan and/or intent) and refusal to contract for safety, 3) psychiatric hospitalization, 4) possible need for psychiatric hospitalization, or 5) significant worsening of depressive or other clinical symptoms (CDRS-R > 76 or CGI improvement score > 5). Adolescents will be removed from the study immediately following review if the *independent safety monitor* deems that the patient requires treatment outside of study protocols or if the treatment provided in the study is contraindicated. In these cases, the family will be provided with referrals to receive treatment out of the protocol.

While fluoxetine is generally well tolerated, side effects can occur. Adverse events will be closely monitored during each psychopharmacological treatment visit using the C-SSRS and the Side Effects forms. The study psychiatrist will review with families the following potential fluoxetine related adverse events: gastrointestinal complaints (nausea, pain, diarrhea, and constipation), dizziness, allergic reactions, increased anxiety or irritability, increased activation/restlessness, sleep changes (increased or decreased), sexual side effects, appetite changes (increase or decrease), unusual thoughts, sweating, fatigue, suicidal ideation/attempts/and or behaviors. In addition to these issues, the study psychiatrist will make the adolescents and their families aware of the Food and Drug Administration advisory that the use of antidepressants like the SSRIs may lead to suicidal thinking/attempts in depressed youths and that the FDA has placed product warning label with information highlighting the need for close observation for worsening of depression and the emergence of suicidality in children treated with these medications. This information will be a part of the consent process for the study so that families are aware of these issues when considering participation in

CONFIDENTIAL

the study. The study psychiatrist will review with the adolescents and their legal guardians, potential adverse events and the need to carefully monitor for any significant changes in mood, thinking, behaviors, and physical symptoms especially early in treatment. The adolescents and their families will be instructed to call the study psychiatrist with any concerns, and to page the PI with any urgent clinical issues that emerge in between treatment sessions. The PI will call the study psychiatrist, who will follow up with the family. In the event of minor side effects (e.g., mild headaches), the medication may be maintained at the current dose levels or reduced. If any adverse medication reactions do occur, the medication will be withdrawn and clinical staff will follow the patient closely until the adverse reaction remits.

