12.1 FUNDING SOURCE27
12.2 CONFLICT OF INTEREST27
12.3 SUBJECT STIPENDS OR PAYMENTS27
13 PUBLICATION PLAN27
14 REFERENCES28

List of Abbreviations

AE	Adverse Event
CC	Cubic Centimeters
CDRS	Children's Depression Rating Scale
CFR	Code of Federal Regulations
CGI	Clinical Global Impressions
CMRR	Center for Magnetic Resonance Research
CRF	Case Report Form
CTSI	Clinical and Translational Science Institute
DSMB	Data and Safety Monitoring Board
DSMP	Data and Safety Monitoring Plan
FDA	Food and Drug Administration
GCP	Good Clinical Practice
HIPAA	Health Insurance Portability and Accountability Act of 1996
IDS	Investigational Drug Services
IRB	Institutional Review Board
KG	Kilogram
K-SADS-PL	Kiddie-Sads-Present and Lifetime
MDD	Major-Depressive Disorder
MEG	Magnetoencephalography
MG	Milligram
ML	Milliliter
MMC	Mayo Mail Code
MRI	Magnetic Resonance Imaging
MRS	Magnetic Resonance Spectroscopy
NOS	Not Otherwise Specified
PET	Positron Emission Tomography
PHA	Phytohemagglutinin
PHI	Protected Health Information
PI	Principal Investigator
SAE	Serious Adverse Event
TRD	Treatment-Resistant Depression
VA	Veterans' Affairs

CONFIDENTIAL

This material is the property of the University of Minnesota. Do not disclose or use except as authorized in writing by the study sponsor

Information Resources

	Name / Address	Phone / Fax / E-mail
Principal Investigator	[name] [name]	[contact] [contact]
Questions concerning eligibility	[name] [name]	[contact] [contact]
For patient enrollment	[name]	
Questions concerning drug ordering, Shipment, transfer or returns	[name]	
Lab shipping or requests	[name]	
Submission of data forms / Questions on data management	[name]	

Study Summary

Title	A Personalized Approach to Achieving a Sustained Response to Treatment for Adolescent Depression
Short Title	PTAD GIA
Protocol Number	1206M15365
Phase	2
Methodology	open label pilot
Study Duration	3 years
Study Center(s)	Single-center
Objectives	To develop and assess the feasibility, acceptability, and preliminary efficacy of a personalized approach to delivering continuation treatment
Number of Subjects	30

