3.1 General Design

Adolescents will receive 16 weeks of continuation treatment. They will be treated by the same clinicians who provided their acute phase treatment. The personalized continuation treatment plan is illustrated below.

Continuation IPT-A. The goal of IPT-A²⁰ is to decrease depressive symptoms by focusing on current interpersonal difficulties and helping the individual improve his or her relationships and interpersonal interactions. This is accomplished through review of the

[figure not shown]
[figure not shown]
adolescent's significant relationships which leads to the identification of the interpersonal problem areas on which to focus the treatment, development of communication and interpersonal problem solving skills, and role-playing. During the Continuation IPT-A sessions, the therapist will continue to emphasize the interpersonal strategies that were learned and practiced during the acute phase, and address any current interpersonal problems before they result in a recurrence of depressive symptoms. Adolescents who have responded to acute phase treatment (CGI-I = much improved or very much improved) will attend 4 biweekly IPT-A sessions followed by 2 monthly sessions. Adolescents who showed a partial response to acute phase treatment (CGI-I = minimally improved) will attend 8 weekly IPT-A sessions followed by 2 monthly sessions.

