Continuation Pharmacotherapy. Adolescents who received fluoxetine during the acute phase and were responders (CGI-I = much improved or very much improved) will continue their acute phase dosing regimen and will meet with the psychiatrist on a monthly basis. Adolescents who received fluoxetine during the acute phase and were partial responders (CGI-I = minimally improved) will enter the continuation phase on 40mg fluoxetine, and will have their dose increased to 60mg.⁴⁰ Partial responders will meet with the psychiatrist biweekly for the first 2 months and monthly for the second 2 months. Adolescents who received only IPT-A during acute phase and were partial responders (CGI-I = minimally improved) will begin treatment with fluoxetine during the continuation phase, in addition to continuing their IPT-A treatment. The dosage schedule will be 10mg per day for the first week and 20mg per day for the following 5 weeks. If no treatment response is observed by the 6th week, the dosage can be increased to 40mg per day.⁴¹ Pharmacotherapy sessions will be scheduled weekly for the first 4 weeks and biweekly thereafter. Pharmacotherapy sessions will include assessment of vital signs, adverse effects, safety, and symptomatic response.

Assessments. Assessments will be administered by independent evaluators who are blind to treatment condition. Adolescents will enter continuation treatment at week 16. Assessments will be conducted at week 24 and 32. The week 32 evaluation is already funded through the K23 study. Assessment measures include the Schedule for Affective Disorders and Schizophrenia for School-aged Children-Present and Lifetime Version (K-SADS-PL),⁴² Children's Depression Rating Scale-Revised (CDRS-R),⁴³ Columbia Suicide Severity Rating Scale (CSSRS),⁴⁴ Global Assessment Scale for Children (C-GAS),⁴⁵ Beck Depression Inventory-II (BDI-II),⁴⁶ Social Adjustment Scale-Self-report (SAS-SR),⁴⁷ Conflict Behavior Questionnaire (CBQ),⁴⁸ and Client Satisfaction Questionnaire (CSQ-8).⁴⁹

CONFIDENTIAL

Treatment Phase	Acute	Continuation	
Assessment	Week 16	Week 24	Week 32

R = Responder (CGI-I = much improved or very much improved), PR = Partial Responder (CGI-I = minimally improved), NR = Nonresponder (CGI-I = no change or worsening)

CONFIDENTIAL

This material is the property of the University of Minnesota. Do not disclose or use except as authorized in writing by the study sponsor

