3.3 Secondary Study Endpoints

The secondary outcome measures include depressive symptoms Children's Depression Rating Scale (CDRS), Children's Global Assessment Scale (C-GAS), Social Adjustment Scale (SAS-SR), and response status as defined by Clinical Global Impressions Scale (CGI).⁵⁰ Responders will be defined as having a 1 or 2 (much or very much improved), partial responders will be defined as having a 3 (minimally improved) whereas non-responders will be defined as having a 4-7 on the CGI (minimally improved to very much worse).

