5.3 Method for Assigning Subjects to Treatment Groups

There is no randomization in this study. Assignment to treatment groups is described above (based on CGI-I score).

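### The CGI response-status endpoint has no named blind rater or time point, and the only CGI-I rating described in continuation is the unblinded therapist's

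*Combined protocol and SAP*

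**What the plan says.** Section 3.3 lists among the secondary outcomes "response status as defined by Clinical Global Impressions Scale (CGI"), with scores of 1 or 2 as responder, 3 as partial responder and 4 to 7 as non-responder. It names neither a rater nor a visit.

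Section 3.1 (Assessments) states: "Assessments will be administered by independent evaluators who are blind to treatment condition". Continuation starts at week 16, and the evaluations fall at weeks 24 and 32, the latter funded through the linked K23 study. The list of measures begins "Assessment measures include the Schedule for Affective Disorders and Schizophrenia for School-aged Children-Present and Lifetime Version (K-SADS-PL") and ends "and Client Satisfaction Questionnaire (CSQ-8"). Between these stand the CDRS-R, C-SSRS, C-GAS, BDI-II, SAS-SR and CBQ. CGI is not named.

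Section 8.4 (Stopping Rules) says that "therapists assess suicidality and change in adolescents' clinical status using the CGI-I and CGI-S at each therapy session". A CGI improvement score above 5 is one of the triggers there for review by the independent safety monitor.

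On the therapists, 3.1 says "They will be treated by the same clinicians who provided their acute phase treatment", and the Study Summary describes the study as an "open label pilot".

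**The concern.** The plan takes care to have outcomes rated by people who do not deliver the treatment. One secondary endpoint appears to fall outside that protection, because its scale is missing from the evaluators' named measures and is described only as a therapist rating. A therapist who has treated the adolescent through the acute phase, knows the continuation plan and hopes it works is not a neutral judge of improvement. With no control group, a shared tendency to rate generously would not cancel out in any comparison.

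What is at stake is the credibility of the response percentages reported at the end of continuation. Unless the source is fixed in advance, a reader of the results could not tell whether those percentages are blind evaluations or treating-clinician ratings.

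**Working it through.** No formula or planned figure is involved. The check sets the sections side by side.

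**1. Which secondary-endpoint scales are in the evaluators' named measures?**

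| Scale in 3.3 | Named in 3.1 (Assessments)? |
|---|---|
| CDRS | Yes |
| C-GAS | Yes |
| SAS-SR | Yes |
| CGI (response status) | No |

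CGI is the only one of the four that is missing.

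**2. Is another CGI rater named for continuation?** Section 6 repeats the week 24 and 32 timing without listing measures. The pharmacotherapy visits in 3.1 and 5.2 cover symptomatic response but name no scale. The key of responder, partial-responder and non-responder categories printed with the week 16/24/32 table in 3.1 uses CGI-I but gives no rater. Only 8.4 names someone who rates CGI-I, and that is the therapist.

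**3. Is the therapist blind?** No. The study is open label, and the therapist delivers the treatment and also delivered the acute phase.

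**4. How many therapist ratings would there be?** From the session schedule in 3.1:
- acute-phase responders: 4 biweekly + 2 monthly = 6 sessions;
- acute-phase partial responders: 8 weekly + 2 monthly = 10 sessions.

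So there are 6 or 10 candidate therapist ratings per adolescent, no rule for choosing among them, and a different number by response class. There are 2 evaluator visits in continuation, and CGI is named at neither.

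**5. Which analyses would be touched?** For Hypotheses 5 and 6, section 7.2 names:
- CDRS, C-SSRS and CGAS (primary);
- BDI-II, CBQ and SAS-SR (secondary);
- recovery and relapse on the K-SADS-PL.

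All seven instruments are in the 3.1 list. Neither 7.2 nor the Study Summary specifies an analysis of CGI response status.

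**6. Can the bias be sized?** Only a rating that crosses the boundary between 2 and 3 changes who counts as a responder; a move from 2 to 1 or from 4 to 3 does not. With all 30 adolescents in the denominator, one such crossing moves the percentage by 1/30 = 3.3 points. If the percentage is taken among acute-phase responders only, as Hypothesis 5 would suggest, the step is 100/n points. That exceeds 3.3 whenever n is below 30, and n is not given. These are step sizes, not bias estimates. The documents say nothing about how often a therapist and a blind evaluator would disagree, or in which direction.

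**The case against.** The strongest case against this has three parts.

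First, the evaluators may already rate CGI-I. The list in 3.1 is introduced by *include*, so it is not declared complete. The week 32 evaluation belongs to the linked study, whose battery is not in these documents. The CGI-I key appears with the table of assessment weeks, and the accompanying figure is not shown. This stands: it cannot be asserted that only therapists rate CGI-I. It does not close the gap, because nothing in the text assigns the endpoint rating to an evaluator.

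Second, the therapist rating in 8.4 is there for monitoring and stopping, and no section says that it supplies the endpoint. This also stands. A reader might infer that the blinding statement in 3.1 is false, but that would follow only if therapist ratings were in fact used.

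Third, the endpoint carries little weight. A reader might infer that the test of sustained response under Hypothesis 5 is compromised. Section 7.2 does not support that, since it tests Hypotheses 5 and 6 on other measures, all in the evaluators' battery. Section 7.1 disclaims an aim of evaluating efficacy, and 3.2 makes feasibility and acceptability primary. This limits the point to one secondary endpoint without removing it, because an endpoint listed in 3.3 should have a stated source.

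A reader might also infer that the evaluators' blind is easily broken, since "Assignment to treatment groups is described above (based on CGI-I score") and the week 16 class therefore reveals the plan. That requires the evaluator to learn the class, and no section describes such disclosure.

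**Conclusion.** The point holds in a limited form. The protocol lists CGI response status as a secondary endpoint without a rater or time point. CGI is not among the measures named for the blind evaluators, and the only CGI-I rating it describes in continuation is the unblinded therapist's, made for session-level monitoring. Followed as written, the plan leaves only therapist ratings available for this endpoint, and expectation could bias them with no control group to offset it.

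This rests on taking the named measures in 3.1 as what will be collected. If the linked study's evaluators already rate CGI-I, the gap is one of wording only.

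The size of any bias cannot be estimated from the documents. A reader might put a figure on it, for instance 3 to 6 of 30 adolescents overrated across the boundary (3/30 = 10 to 6/30 = 20 points). That disagreement rate would be an assumption with nothing in the documents behind it, and 30 is not the denominator for Hypothesis 5. The primary feasibility outcomes and the measures that 7.2 names for Hypotheses 5 and 6 are unaffected. The change is still worth making, because a blind evaluation already takes place at each of the two visits.

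**What to change.** In 3.1, add CGI-I and CGI-S to the independent evaluators' measures at weeks 24 and 32. In 3.3, state that response status uses the evaluator's CGI-I at those visits. State also, in 3.3 or 8.4, that the therapist's session ratings serve safety monitoring only and do not supply the endpoint. The monitoring and withdrawal provisions in 4.4.1 and 8.4 and the treatment rules stay as they are.

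The cost is an amendment and a brief global rating added to an evaluation that already takes place. Week 32 needs coordination with the linked study that funds it, since its procedures may have to change too. If evaluators already rate CGI-I there, all that is needed for that visit is to name their rating as the source of the endpoint.

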8.5 Medical Monitoring

It is the responsibility of the Principal Investigator to oversee the safety of the study at his/her site. This safety monitoring will include careful assessment and appropriate reporting of adverse events as noted above, as well as the construction and implementation of a site data and safety-monitoring plan (see section 9 Auditing, Monitoring and Inspecting). Medical monitoring will include a regular assessment of the number and type of serious adverse events.

8.5.1 Internal Data and Safety Monitoring Board

The PI will maximize the safety and privacy of all study participants and ensure the integrity, validity, and confidentiality of data collection procedures through regular monitoring of clinical and research activities during weekly project meetings with the study staff. At the start of each treatment session, clinicians will be required to ask both adolescents and parents whether any adverse events or suicidality have occurred in the past week. Clinicians will report to the PI any serious or unexpected adverse events, unexpected problems that involve risk to the participants or others, and any breaches of confidentiality. The PI will report these to the Quorum within 24 hours of their occurrence. The PI will also submit an annual progress report to the IRB summarizing the data and safety monitoring activities and outlining 1) whether participants' safety, privacy and confidentiality has been consistently assured, 2) whether research instruments have been administered in a uniform manner and in a way that protects participants' privacy, 3) progress towards recruitment goals, quality of data collection (e.g., appropriate completion of forms), and participant retention/ attrition rates, and 4) a review of new scientific literature pertinent to the safety of participants or the ethics of research participation. The study psychiatrists, *the independent safety monitor*, psychologists, research clinicians, and clinical interviewers will take all appropriate actions to prevent and treat psychiatric emergencies in participating adolescents and family members as outlined in the Procedures to Minimize Potential Risks.

On an annual basis, the PI and [name] will monitor the safety, quality and conduct of this study and decide whether adequate subject safeguards are in place. They will review: 1) the progress of the proposed study, including assessments of data quality and participant recruitment, accrual and retention; 2) outcome and adverse event data to determine whether there is any change to the anticipated benefit-to-risk ratio of study

CONFIDENTIAL

participation and whether the study should continue, be changed, or terminated; 3) external factors or relevant information (e.g., pertinent scientific literature reports or therapeutic developments, results of related studies) that may have an impact on the safety of study participants or the ethics of the research study; and 4) study procedures designed to protect the privacy of the research subjects and the confidentiality of their research data.

9 Data Handling and Record Keeping

